#### 9.2 Analysis Populations

The following populations will be considered for analysis of various endpoints:

Randomized Set: It includes all randomized subjects who satisfied the inclusion and exclusion criteria described in this protocol

Full Analysis (or Intent-to-Treat [ITT]) Set: It is the analysis population for the primary efficacy analysis. It includes all randomized subjects classified according to the treatment arm into which they were randomized regardless of the actual treatment received.

Per Protocol Set: It includes all subjects in the Full Analysis (or ITT) Set who satisfy COVID-19 disease criteria at baseline without any major protocol deviations which may affect the evaluation of the primary efficacy endpoints

Safety Set: It includes all randomized subjects, classified according to the actual treatment received regardless of randomization assignment, who received any amount of study drug and have at least one post-baseline safety evaluation. This is the analysis population for all planned safety analyses.

Pharmacokinetic (PK)-Evaluable Set: It consists of all randomized subjects, classified according to the actual treatment received regardless of randomization assignment, who receive at least one dose of study drug. A baseline and at least one pharmacokinetic blood sample following a dose of study treatment is required for inclusion in this analysis set. This is the analysis population for all planned pharmacokinetic analyses.

#### 9.3 Planned Analyses

The analyses described in this section will be performed for data captured in Study Part 1 and Study Part 2 separately. No formal statistical inference is planned for data captured in Study Part 1.

As a general strategy, continuous efficacy and safety endpoints will be summarized using the five-number summary (mean, standard deviation, median, minimum, and maximum). Frequency distributions (counts and percentages) will be used to summarize categorical endpoints.

#### 9.3.1 Disposition of the Study Participants

The disposition of subjects will be described with summaries by treatment group of the number of subjects in each analysis set described above, the number of subjects who completed the study (including the reasons for withdrawal), and the number of subjects for whom study drug was permanently discontinued (including the reasons for discontinuation). The ITT set will be used to produce this analysis.

#### 9.3.2 Demographic and Baseline Disease Characteristics

Demographic and baseline disease characteristics will be summarized and compared by treatment group. Results will be reported using subjects in the ITT Analysis Set.

Medical history will be coded and reported by system organ class and body system.

Prior medications will be classified according to the anatomical therapeutic chemical (ATC) codes in the World Health Organization Drug (WHODRUG) dictionary. The incidence rate of each classified medication will be tabulated by treatment group. Tables will be sorted by the incidence use of the entire sample.

#### 9.3.3 Exposure to Study Treatment and Compliance

Frequency distributions of the number of doses received will be presented by treatment group. Treatment duration and treatment compliance for all randomized subjects will also be described by treatment group.

Concomitant medications will be classified and reported in a manner similar to prior medications.

#### 9.3.4 Analysis of Primary Efficacy Endpoints of Study Part 2

The primary efficacy endpoint in Study Part 2 is median time (in hours) to hospital discharge where discharge is defined as a score of 1 or 2 in the 8-point WHO Ordinal Scale for Clinical Improvement score. It is defined as the number of days from randomization to the first occurrence of discharge from the hospital (e.g., clinical recovery).

Median time (in hours) to hospital discharge and corresponding 95% confidence intervals will be estimated using the Kaplan-Meier method. Additionally, Cox proportional hazards model, with randomization factors as covariates, will be used to estimate the hospital discharge rate and corresponding 95% confidence interval. P-value will also be reported.

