### 4 STUDY PLAN

### 4.1 Study Design

This is a 2-part, multicenter, randomized, placebo-controlled clinical study of ANA001 in patients with moderate and severe COVID-19. The study duration for each participant will be approximately 62 days, including a 36-hour screening window. Screening and Day 1 may occur on the same day if screening criteria is met to confirm subject eligibility. Randomization of subjects will be stratified by oxygenation (SpO2 >93 and <98% on room air versus SpO2  $\leq$ 93% on room air), diarrhea (presence versus absence), and age ( $\leq$ 65 and  $\geq$ 65).

The Sponsor will review blinded safety data on an ongoing basis, and an independent Data Monitoring Committee (DMC) will review available unblinded safety and efficacy data in accordance with the DMC Charter.

Part 1 will primarily evaluate safety and tolerability of ANA001 compared with matching placebo and explore PK parameters. Blood samples (Primary and Back-Up) for PK are to be collected on Day 1, 2, 3 or Day 4 at pre-dose (i.e. within 30 minutes), 1 hour (+/-30 minutes), 4 hour (+/- 30 minutes), 8 hour (+/- 30 minutes) and pre-dose to next study drug (i.e. within 30 minutes) administration.

Part 2 will evaluate safety, tolerability, and efficacy of the proposed clinical dosing regimen of ANA001 as compared with matching placebo.

After provision of informed consent, participants who satisfy all inclusion and no exclusion criteria will be dosed within 36 hours of screening and as soon as possible following hospital presentation.

### Part 1

Participants in Part 1 will be randomly assigned to either ANA001 or matching placebo in a 1:1 ratio. Participants will receive capsules of ANA001 or matching placebo for 7 consecutive days (defined as 14 doses administered BID) according to the assignment made by the randomization and trial supply management (RTSM) system. Additionally, participants will receive continued standard-of-care (SOC) therapy (per study site policies or guidelines).

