#### 9.1 Determination of Sample Size

#### **9.1.1 Study Part 1**

60 participants (30 randomized to ANA001 and 30 to placebo) are anticipated to provide sufficient data to assess safety and tolerability of ANA001 in patients with moderate and severe COVID-19. The sample size is based on clinical consideration and is consistent with the size of other studies with similar objectives.

#### **9.1.2** Study Part 2

One study reported that subjects treated with placebo will have a median time to clinical improvement around 15 days (Beigel *et al.*, 2020). Treatment with ANA001 is expected to reduce median time to clinical improvement to 11 days. At least 374 recoveries must be achieved for a log rank test to have 85% power at a two-sided significance level of 0.05.

Assuming a 6 months accrual period and the last enrolled subject will be followed for 30 days, at least 376 subjects must be randomized in 1:1 ratio. That is, at least 188 subjects must be randomized to be treated with ANA001 and 188 subjects to be treated with placebo.

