4.4 Covariates

Sample size permitting, the following randomization factors will be considered as covariates:

- Oxygenation (SpO2 > 93 and < 98% on room air, \leq 93% on room air)
- Diarrhea (presence, absence), and
- Age at screening ($<65, \geq 65$).

Additionally, baseline score of the WHO Clinical Improvement Scale and the number of coexisting conditions will be used as covariates.

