7.4. Efficacy Analysis for Secondary Endpoint

The secondary efficacy endpoint for Part 1 of this study is the median time (in hours) from randomization to hospital discharge (where discharge is defined as a score of 1 or 2 in the WHO Ordinal Scale for Clinical Improvement).

Kaplan-Meier curves will be constructed to display time-to- hospital discharge. Participants who are lost to follow-up or ended study early prior to achieving clinical improvement will be censored at the day of the last obtained assessment of their WHO Ordinal Scale for Clinical Improvement. Participants who complete follow-up without hospital discharge will be censored at the day of their Day 60 visit. Participants who die for any reason during the study will be right-censored at Day 60 or date of death, whichever is earlier. For the analysis of this efficacy endpoint, missing scores of the WHO Ordinal Scale for Clinical Improvement will be assumed to be > 2 (*i.e.*, no hospital discharge). Median time-to-clinical improvement and corresponding 95% confidence interval will be estimated from the Kaplan-Meier curves and tabulated for each treatment group.

The Cox proportional hazard method will be used to calculate the hospital discharge rate ratio of ANA001 relative to placebo while controlling for the stratification factors, baseline WHO Ordinal Scale for Clinical Improvement, and number of co-existing conditions. Hospital discharge rate ratio is akin to a hazard ratio but for the beneficial outcome of hospital discharge.

A hospital discharge rate ratio > 1 indicates a benefit for ANA001. Treatment groups will be compared using a stratified log-rank test.

The above analyses will be produced for all participants in the Full Analysis Set and by baseline WHO Ordinal Scale for Clinical Improvement scores. Additionally, the same analysis will be produced for participants in the Per-Protocol Analysis Set and Safety Analysis Set.

If WHO Ordinal Scale are missing at baseline, 6 hours window after first dose will be added for baseline values.

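### The Part 2 Cox model for time to discharge omits the baseline WHO score, which the Part 1 SAP uses for the same endpoint, and so may give up some efficiency

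*Protocol*

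**What the plan says.** Protocol 9.3.4 estimates median time to discharge by Kaplan-Meier and then adds the Cox model: "Additionally, Cox proportional hazards model, with randomization factors as covariates, will be used to estimate the hospital discharge rate". A p-value is to be reported, but no test is named as primary. The randomization factors are set in Protocol 4.1 ("Randomization of subjects will be stratified by oxygenation", then diarrhea and age).

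The SAP supplied covers Part 1 only. For the same endpoint, SAP 7.4 fits a Cox model "controlling for the stratification factors, baseline WHO Ordinal Scale for Clinical Improvement, and number of co-existing conditions", and then compares the groups with a stratified log-rank test. SAP 4.4 lists the extra covariates in general terms: "Additionally, baseline score of the WHO Clinical Improvement Scale and the number of coexisting conditions will be used as covariates".

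The Part 2 sample size in Protocol 9.1.2 rests on a log-rank test with no covariates mentioned: "At least 374 recoveries must be achieved for a log rank test to have 85% power at a two-sided significance level of 0.05".

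The WHO score is scheduled at screening and on Day 1 for everyone (Protocol Table 1, 6.1 and 6.3.1).

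**The concern.** The endpoint is reaching score 1 or 2 on a scale whose starting value is known for each participant, yet the confirmatory part does not adjust for that value. The 60-participant part, for which Protocol 9.3 plans no formal inference, has the fuller model; the 376-participant part has the thinner one. The protocol also departs from its own practice, since 9.3.5 adjusts continuous secondary endpoints for their baseline values.

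In a Cox model, omitting a covariate that predicts the outcome pulls the treatment ratio toward 1, even when the arms are balanced on it, and lowers power. The oxygenation stratum covers part of the same ground but not all of it. It is defined by room-air SpO2, whereas scores 4 and 5 in Protocol Appendix 1 differ by need for supplemental oxygen. What is at stake is some power, and a slightly diluted rate ratio, that a variable already collected could recover.

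**Working it through.** **Inputs from Protocol 9.1.2.** Placebo: "will have a median time to clinical improvement around 15 days". Active: "Treatment with ANA001 is expected to reduce median time to clinical improvement to 11 days". Two-sided 0.05, power 85%, 374 events, 376 participants at 1:1. Timing: "Assuming a 6 months accrual period and the last enrolled subject will be followed for 30 days".

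**The plan's own figure.** Under exponential times the discharge rate ratio is 15/11 = 1.364. Schoenfeld's formula gives 4 × (1.960 + 1.036)² / (ln 1.364)² = 373.3, rounded up to 374. This matches the stated number, and power at 374 events is 85.1%. With uniform 6-month accrual and at least 30 days of follow-up, the average event probability is 0.978, so 374 / 0.978 = 382 participants against the stated 376, a difference of 1.6%. No covariate enters this calculation.

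**Effect of adding the score.** The documents give no effect of baseline score on discharge, so this part is a simulation over assumed values:

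- N = 376, allocated 1:1; follow-up to Day 60; overall medians 15 and 11 days; 1,500 runs per row.
- Half the participants at score 4 and half at score 5; 25% with diarrhea, without effect; an age effect with rate ratio 1.3.
- No effect of SpO2 beyond the score; no deaths or dropout.
- Agreement is the share of participants whose SpO2 stratum matches their score. At 50% the stratum says nothing about the score.

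| Discharge rate ratio, score 4 vs 5 | Agreement | Power, three factors | Power, three factors + WHO score | Gain (points) |
|---|---|---|---|---|
| 1.0 | 50% | 80.6% | 81.0% | 0.4 |
| 1.0 | 70% | 84.4% | 84.3% | -0.1 |
| 1.0 | 90% | 82.7% | 82.1% | -0.6 |
| 1.5 | 50% | 80.6% | 84.7% | 4.1 |
| 1.5 | 70% | 81.8% | 83.2% | 1.4 |
| 1.5 | 90% | 81.7% | 82.8% | 1.1 |
| 2.0 | 50% | 74.9% | 81.6% | 6.7 |
| 2.0 | 70% | 77.5% | 82.5% | 5.0 |
| 2.0 | 90% | 80.2% | 82.3% | 2.1 |
| 3.0 | 50% | 65.3% | 81.7% | 16.4 |
| 3.0 | 70% | 67.6% | 82.4% | 14.8 |
| 3.0 | 90% | 75.4% | 81.3% | 5.9 |

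Each power has a standard error of about √(0.8 × 0.2 / 1500) = 1.0 point. Both models were fitted to the same data sets, so the gain within a row is steadier than comparisons between rows. At a ratio of 2.0 the average estimated treatment ratio was 1.33 to 1.35 without the score and 1.37 with it.

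**The levels are not a forecast.** With follow-up to Day 60 the expected events are 376 × (0.9375 + 0.9772) / 2 = 360, for which Schoenfeld gives 83.7%. That is a separate matter from the covariates. The lower three-factor powers at ratios of 2.0 and 3.0 arise because the simulation applies 15/11 among participants with the same covariates, while the planning formula applies it overall. Only the differences bear on this point.

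**Scale of the gain.** Required events vary with (1.960 + z for power)². Moving from 80% to 82% is (2.875 / 2.802)² = 1.05, or 5% more events. Moving from 75% to 82% is (2.875 / 2.635)² = 1.19, or 19% more.

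**Sensitivity to score 6.** In further runs with agreement of 70% to 90%, rates at scores 5 and 6 of 0.55 and 0.30 relative to score 4, and 10% of participants at score 6, the gain was 5.0 to 7.5 points. With scores 4 and 5 only (40/60) and the same 0.55, it was 2.6 to 2.8 points; at 0.7 it was 0.8 to 1.7 points.

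**The case against.** The strongest reply is that adjusting for the stratification factors alone is a valid and conventional choice, that nothing in the documents shows the score to be prognostic, and that a Part 2 SAP is still to come (Protocol section 9) and may set the covariates. The first two parts stand: the gain is conditional, and there is no error of validity. The third stands only in part. A later SAP could add the score, but the covariate set now written in 9.3.4 would still have to be reconciled with it.

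A reader might infer a larger loss by supposing that many participants start at score 6. Protocol 5.4, exclusion 3, removes noninvasive ventilation and high-flow oxygen above its stated thresholds, so few can start there. The sensitivity runs show that about half of the gain in such a scenario comes from that group.

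A reader might also infer that the primary p-value comes from the Cox model, so that its covariates decide the trial. The protocol does not say so. It powers a log-rank test, introduces the Cox model as an addition, and names no primary test. If the log-rank test is primary, the Cox covariates affect the reported ratio but not that p-value.

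**Conclusion.** The point holds as an improvement, with a modest and uncertain size. Protocol 9.3.4 leaves out a baseline variable that is already collected and that SAP 7.4 uses for the same endpoint. With participants mainly at scores 4 and 5, adding it gains about nil if the score is not prognostic and about 1 to 7 percentage points at a discharge rate ratio of 1.5 to 2.0. The upper end requires an SpO2 stratum that carries no information about the score; at 70% to 90% agreement the range is about 1 to 5 points. A ratio of 3.0 would give about 6 to 16 points, but nothing in the documents supports a value that high, or any other particular value.

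It would be tempting to conclude that the trial misses its 85% power for this reason, or that the baseline score is the best predictor of discharge. The documents support neither. The 374 events and 85% come from an unadjusted log-rank calculation that never relied on the score, and no document ranks the predictors.

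**What to change.** In Protocol 9.3.4 and the Part 2 SAP, add the last pre-dose WHO score to the randomization factors as a prespecified Cox covariate, in line with SAP 7.4.

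- State its levels. SAP 5.2 lists baseline scores 3 and 4 as subgroups, which does not fit participants mainly at 4 and 5 on the Appendix 1 scale.
- State the rule for a missing score. SAP 7.4 accepts a value up to 6 hours after the first dose, which is no longer pre-dose.
- Name the one test that gives the primary p-value. Protocol 9.1.2 powers a log-rank test, 9.3.4 names only a Cox model, and SAP 7.4 compares groups with a stratified log-rank test. The hierarchy in Protocol 9.7 opens only on that result.
- Adding the number of co-existing conditions is optional. It was not simulated, and its count in SAP 4.1 includes age over 60, which overlaps the age stratum.

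The cost is a sentence or two in each document before unblinding, with no new data. The small downside is that the reported ratio becomes conditional on one more covariate.

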#### 9.3.5 Analysis of Secondary Efficacy Endpoints

Mean change from baseline in continuous secondary efficacy endpoints will be compared using an analysis of variance model with baseline values and stratification factors as covariates. Difference in least-squares means and associated 95% confidence intervals will be reported. Sample size permitting, P-values will also be reported.

Logistic regression models, with stratification factors as covariates, will be used to compare categorical secondary endpoints. Odds ratio and corresponding 95% confidence intervals will be reported. P-values will also be reported.

#### 9.3.6 Safety Analysis

All safety endpoints will be summarized using data from the safety set. Safety analyses will involve examination by treatment group of the incidence, relatedness, severity and type of treatment-emergent adverse events reported, changes from baseline (the assessment prior to first dose) in laboratory test results and in vital signs to specified timepoints throughout the study. Concomitant medications use will also be summarized by treatment group.

#### 9.3.6.1 Treatment-Emergent Adverse Events

All adverse events reported during the study will be coded using a MedDRA (v21.1) dictionary. Non-treatment-emergent AEs will be captured on the appropriate eCRF and a listing will be generated for the randomized set. Only treatment-emergent AEs (TEAEs) will be summarized in the planned safety analyses. The incidence of treatment-emergent adverse events will be summarized by treatment group and the following:

Preferred term

System organ class and preferred term

System organ class, preferred term and severity

These summaries will be presented for the following subsets:

All adverse events

Serious adverse events

Drug-related adverse events

Adverse events leading to study treatment discontinuation.

For tables reporting adverse events by severity, if a subject has multiple occurrences of an adverse event with the same organ class and preferred term, the most severe event will be presented.

#### 9.3.6.2 Clinical Laboratory Evaluation

Safety laboratory parameters will be summarized by treatment group at each visit. Each summary will include the values of the laboratory parameters and their change from baseline.

Shift tables from baseline will be presented for laboratory values in the hematology, chemistry, and coagulation tests. Parameters will be classified according to the laboratory reference normal ranges. A listing will be provided for out of normal range as well as potentially clinically significant abnormal laboratory values.

#### 9.3.6.3 Vital Signs

Vital signs, including pulse, respiratory rate, blood pressure (i.e., systolic and diastolic), and temperature will be summarized by treatment group and timepoint. For each assessment of vital signs, change and percent change in vital signs from baseline will be summarized by treatment group.

#### 9.4 **Interim Analysis**

Upon completion of Study Part 1, the independent DMC will conduct a review of safety and efficacy data to provide potential recommendations for early termination or possible study adaptations as outlined in the DMC charter. Additional details regarding interim analyses are outlined in the DMC statistical analysis plan (SAP) and the study SAP.

#### 9.5 **Independent Data Monitoring Committee**

An independent Data Monitoring Committee (DMC) will be formed and constituted according to appropriate regulatory agency guidelines. Detailed information regarding the composition of the committee and detailed procedures will be provided in a separate DMC charter. The independent DMC will review the safety, tolerability, and efficacy data of Study Part 1 and Study Part 2 as described in the DMC charter.

#### 9.6 **Handling of Missing Data**

Missing efficacy assessments will be imputed using a multiple imputation method appropriate to the pattern of missingness. Details of the considered patterns and associated sensitivity analyses will be described in the Statistical Analysis Plan.

#### 9.7 **Multiplicity Adjustment**

A hierarchical testing scheme is planned to preserve the familywise type I error of the study. If statistical significance of the primary efficacy endpoint is established, secondary efficacy endpoints will be tested in the following order:

- 1. Mean change from baseline (BL) in National Early Warning Score (NEWS2)
- 2. Mean number of days on rescue treatment (COVID-19 treatments that are approved under NDA or EUA) within 15 days after enrollment

The testing scheme will be halted at the first secondary endpoint that fails to establish statistical significance.

#### 9.8 **Pharmacokinetic Analysis**

Descriptive statistics of individual plasma concentrations for ANA001 will be summarized and listed according to the sampling schedule outlined in Appendix 6 for Study Day 1, 2, 3, or 4 for the PK-Evaluable set and will be reported in the CSR.

Derived PK parameters, population PK analyses, and potential pharmacokinetic/pharmacodynamic (PK/PD) relationships will be reported separately.

#### 10 ETHICAL CONSIDERATIONS

#### 10.1 Good Clinical Practice

This study will be conducted in compliance with Good Clinical Practices (GCP), i.e., International Council for Harmonization (ICH) of Technical Requirements for Pharmaceuticals for Human Use guideline E6 (R2) on Good Clinical Practice, other ICH guidelines, and relevant national guidelines on GCP.

